## 8.0 Adverse Event (AE) Monitoring and Reporting

The site principal investigator is responsible for reporting any/all serious adverse events to the sponsor as described within the protocol, regardless of attribution to study agent or treatment procedure

The sponsor/sponsor-investigator is responsible for notifying FDA and all participating investigators in a written safety report of any of the following:

- Any suspected adverse reaction that is both serious and unexpected.
- Any clinically important increase in the rate of a serious suspected adverse reaction over the rate stated in the protocol or Investigator's Brochure (IB).
- Any findings from laboratory animal or *in vitro* testing that suggest a significant risk for human subjects, including reports of mutagenicity, teratogenicity, or carcinogenicity.
- Any findings from epidemiological studies, pooled analysis of multiple studies, or clinical studies, whether or not conducted under an IND and whether or not conducted by the sponsor, that suggest a significant risk in humans exposed to the drug.

## Definitions

### *Adverse Event*

Any untoward medical occurrence associated with the use of a drug in humans, whether or not considered drug related.

### *Suspected Adverse Reaction*

Any adverse event for which there is a reasonable possibility that the drug caused the adverse event.

### *Expedited Reporting*

Events reported to sponsor within 24 hours, 5 days or 10 days of study team becoming aware of the event.

### *Routine Reporting*

Events reported to sponsor via case report forms

### *Events of Interest*

Events that would not typically be considered to meet the criteria for expedited reporting, but that for a specific protocol are being reported via expedited means in order to facilitate the review of safety data (may be requested by the FDA or the sponsor).

## 8.1 Adverse Event Characteristics

**CTCAE term (AE description) and grade:** The descriptions and grading scales found in the revised NCI Common Terminology Criteria for Adverse Events (CTCAE) version 5.0 will be utilized for AE reporting. All appropriate treatment areas should have access to a copy of the CTCAE version 5.0. A copy of the CTCAE version 5.0 can be downloaded from the CTEP web site:

- a. Adverse event monitoring and reporting is a routine part of every clinical trial.
- b. Identify the grade and severity of the event using the CTCAE version 5.0.
- c. Determine whether the event is expected or unexpected (see Section 8.2).
- d. Determine if the adverse event is related to the study intervention (agent, treatment or procedure) (see Section 10.3).

- e. Determine whether the event must be reported as an expedited report. If yes, determine the timeframe/mechanism (see Section 8.4).
- f. Determine if other reporting is required (see Section 8.5).
- g. Note: All AEs reported via expedited mechanisms must also be reported via the routine data reporting mechanisms defined by the protocol (see Sections 8).

Each CTCAE term in the current version is a unique representation of a specific event used for medical documentation and scientific analysis and is a single MedDRA Lowest Level Term (LLT).

NOTE: A severe AE, as defined by the above grading scale, is NOT the same as serious AE which is defined in the table in Section 8.4.

## 8.2 Expected vs. Unexpected Events

*Expected events* - are those described within the Section 11.0 of the protocol, the study specific consent form, and the investigator brochure, (if an investigator brochure is not required, otherwise described in the general investigational plan).

*Unexpected adverse events* or suspected adverse reactions are those not listed in Section 11.0 of the protocol, the study specific consent form, or in the investigator brochure (or are not listed at the specificity or severity that has been observed); if an investigator brochure is not required or available, is not consistent with the risk information described in the general investigational plan.

*Unexpected* also refers to adverse events or suspected adverse reactions that are mentioned in the investigator brochure as occurring with a class of drugs but have not been observed with the drug under investigation.

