**Less common known potential toxicities 1-10%:**

Dermatologic: Skin rash

Gastrointestinal: Nausea

Hematologic & oncologic: Decreased hemoglobin, lymphocytopenia, prolonged prothrombin time

Hepatic: Increased ALT, increased AST

Hypersensitivity: Hypersensitivity reaction

Frequency not defined:

Hepatic: Increased serum alkaline phosphatase

Hypersensitivity: Anaphylaxis, angioedema

Local: Erythema at injection sites

Miscellaneous: Infusion related reaction

Postmarketing:

Cardiovascular: Bradycardia, heart failure, hypotension

Hepatic: Acute hepatic failure

11.3.8 Drug procurement: Commercial supplies. Pharmacies or clinics shall obtain supplies from normal commercial supply chain or wholesaler.

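### Section 8.2 judges whether an event is unexpected against all of Section 11.0, including background remdesivir's toxicities, so a few serious reactions suspected from camostat can miss the individual safety report in 8.0

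*Combined protocol and SAP*

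**What the plan says.** Section 8.0 lists what the sponsor must report in writing to FDA and the participating investigators. The first item is "Any suspected adverse reaction that is both serious and unexpected". The second is a clinically important rise in the rate of a serious suspected reaction "over the rate stated in the protocol" or the investigator's brochure.

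Section 8.2 supplies the test. Unexpected events "are those not listed in Section 11.0 of the protocol, the study specific consent form, or in the investigator brochure", and a listed event still counts as unexpected if it occurs with greater specificity or severity than listed. A last sentence adds class effects that the brochure mentions "but have not been observed with the drug under investigation".

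Section 11.0 has three parts: camostat (11.1, toxicities at 11.1.7), placebo (11.2, no toxicity list) and remdesivir (11.3, toxicities at 11.3.7). The Schema treats remdesivir as a standard-of-care drug that the study does not provide. Among the postmarketing entries in 11.3.7 are "Cardiovascular: Bradycardia, heart failure, hypotension" and "Hepatic: Acute hepatic failure".

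**The concern.** Whether an event is expected should be judged against what is known of the drug suspected of causing it. Section 8.2 refers to the whole of Section 11.0 and does not restrict it to camostat or to the suspected agent. A new serious reaction to camostat could therefore be treated as already known because a background drug is known to cause it. What is at stake is the prompt report to FDA and to investigators at other sites. The efficacy comparison is not affected.

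**Working it through.** The plan states no figure on this point and no formula applies. The check traces the definitions and compares the two toxicity lists.

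**Step 1: the chain of definitions.** The first trigger in 8.0 needs three things: suspected, serious, unexpected. Unexpected under 8.2 means absent from Section 11.0, the consent form and the brochure alike. Presence anywhere in Section 11.0 is therefore enough to fail the test, and 11.3.7 is part of Section 11.0. No other section limits the list to camostat.

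**Step 2: the 19 terms in 11.3.7 against 11.1.7.**
- No camostat entry (6): raised glucose, prolonged prothrombin time, raised alkaline phosphatase, angioedema, bradycardia, heart failure.
- Only a broader or different camostat term (5): creatinine clearance, hemoglobin, lymphocytopenia, hypotension, acute hepatic failure.
- Infusion or injection site (2).
- Shared (6): rash, nausea, ALT, AST, hypersensitivity, anaphylaxis.

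Check: 6 + 5 + 2 + 6 = 19.

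**Step 3: which terms could matter as serious reactions suspected from camostat.**

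| Term in 11.3.7 | Nearest entry in 11.1.7 | Judged against 11.0 | Judged against 11.1 only |
|---|---|---|---|
| Heart failure | none | not unexpected | unexpected |
| Bradycardia | none | not unexpected | unexpected |
| Acute hepatic failure | hepatic function disorder, jaundice, raised AST/ALT | not unexpected | unexpected, by the specificity and severity clause |
| Angioedema | anaphylactic symptoms, edema | not unexpected | arguable |
| Hypotension | shock | not unexpected | largely overlaps |
| Glucose, prothrombin time, alkaline phosphatase | none | not unexpected as listed | unexpected, but seldom serious as a laboratory finding alone |

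The last two columns assume that the brochure and consent form do not list the event for camostat.

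**Step 4: the safeguards inside 8.2.** The specificity and severity clause does not rescue acute hepatic failure, because the remdesivir list names it outright. The last sentence of 8.2 reaches only class effects mentioned in the brochure, so it does not remove another drug's list in Section 11.0. Section 8.2 also joins its three sources with *and* when defining expected events. If that means all three, an event listed only under 11.3 is neither expected nor unexpected, and it still misses a trigger that requires unexpected.

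**Step 5: the rate trigger in 8.0.** For the clearest cases it offers little: 11.1.7 has no entry, hence no rate, for heart failure, bradycardia or acute hepatic failure, and the postmarketing entries for remdesivir carry none either. Where both drugs list an event, Section 11.0 gives two rates. For raised ALT and AST, nausea and rash, these are 0.1 to below 0.5% for camostat and 1-10% for remdesivir (for example "Hepatic: Increased ALT, increased AST"). The bullet does not say which one applies.

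**The case against.** The strongest reply is that the harmful reading is not the natural one. A suspected adverse reaction is defined by whether the drug caused the event, 8.4 is headed for IND/IDE agents, Section 11.0 is subdivided by drug, and the last sentence of 8.2 speaks of the drug under investigation. A careful sponsor would probably judge camostat against 11.1. That stands as a reason to call this a wording fault. It does not remove the fault: the operative sentence names all of Section 11.0, the table in 7.1 lists remdesivir as an agent, and 8.3 grades attribution to the agent or agents without separating them.

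The reply also narrows the list. 11.3.7 gives no grades, so an unusually severe instance could be argued to exceed what is listed. Laboratory terms such as those in "Decreased hemoglobin, lymphocytopenia, prolonged prothrombin time" would rarely be serious as listed. Prolonged prothrombin time would matter mainly as bleeding, which Section 11.0 does not list and which therefore stays unexpected under that section. Angioedema and hypotension partly overlap camostat's entry for shock and anaphylactic symptoms.

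Other routes do not depend on the Section 11.0 list. Sites report every serious event to the sponsor whatever its attribution (8.4). Expedited reports go to the drug supplier within 24 hours of receipt (8.4.1, special instructions). The fourth bullet of 8.0 requires the same written report for clinical-study findings that suggest a significant human risk. Section 8.5.1 has its own test of unexpectedness by nature, severity or frequency. The DSMB reviews safety (13.7), and adverse events are assessed between arms at the interim analyses (13.1, 13.4). All of this stands. It leaves one gap: the prompt report of an individual serious event to FDA and other investigators.

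**Conclusion.** The point holds as a minor one. Read literally, 8.2 misclassifies a few serious events suspected from camostat: heart failure, bradycardia and acute hepatic failure most clearly, angioedema arguably. The assumptions are the literal reading of Section 11.0, attribution of the event to camostat, and absence of the event for camostat from the brochure and consent form, which cannot be checked here.

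Three stronger inferences are not supported:
- **That camostat safety data would be lost or hidden from oversight.** The routes above keep them.
- **That the chance of a missed report can be calculated.** One could assume a rate of such events and compute the chance of at least one among the 132 patients in the camostat arm. No such rate is in the documents, and the result would be the chance of an event. A missed report also needs attribution to camostat, a match in specificity and severity, the literal reading, and absence from the two unseen documents.
- **That the two rates for ALT and AST can be turned into a size for the problem.** The trigger concerns serious reactions, the listed rates are not specific to serious events, and entry allows ALT or AST up to 5 times the upper limit of normal. The two rates show only that the reference is ambiguous.

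**What to change.** In both defining sentences of 8.2, replace *Section 11.0* by *Section 11.1 (camostat)*, and limit consent-form risks to those stated for camostat. Add: *Listing under 11.3 (remdesivir) does not make an event expected for camostat/placebo; an event possibly due to either is judged against 11.1.* In the second bullet of 8.0, refer to the rate stated for camostat in Section 11.1 or the investigator's brochure.

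The cost is a few edited sentences and some extra safety reports, part of which may prove due to remdesivir or to COVID-19 itself. Sample size and analysis do not change.

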## 8.3 Assessment of Attribution

When assessing whether an adverse event is related to a medical treatment or procedure, the following attribution categories are utilized:

- Definite - The adverse event is *clearly related* to the agent(s).
- Probable - The adverse event is *likely related* to the agent(s).
- Possible - The adverse event *may be related* to the agent(s).
- Unlikely - The adverse event is *doubtfully related* to the agent(s).
- Unrelated - The adverse event is *clearly NOT related* to the agent(s).

**Events determined to be possibly, probably or definitely attributed to a medical treatment suggest there is evidence to indicate a causal relationship between the drug/device and the adverse event.**

## 8.4 Expedited Adverse Event Reporting Requirements for IND/IDE Agents

**8.4.1 Expedited Reporting via the Adverse Event Expedited Report Form** for Adverse Events That Occur Within 30 Days of the Last Dose of the Investigational Agent

**FDA REPORTING REQUIREMENTS FOR SERIOUS ADVERSE EVENTS (21 CFR Part 312)**

**NOTE:** Investigators **MUST** immediately report to the sponsor **ANY** Serious Adverse Events, whether or not they are considered related to the investigational agent(s)/intervention (21 CFR 312.64)

An adverse event is considered serious if it results in **ANY** of the following outcomes:

- 1) Death
- 2) A life-threatening adverse event
- 3) An adverse event that results in inpatient hospitalization or prolongation of existing hospitalization for  $\geq$  24 hours
- 4) A persistent or significant incapacity or substantial disruption of the ability to conduct normal life functions
- 5) A congenital anomaly/birth defect.
- 6) Important Medical Events (IME) that may not result in death, be life threatening, or require hospitalization may be considered serious when, based upon medical judgment, they may jeopardize the patient or subject and may require medical or surgical intervention to prevent one of the outcomes listed in this definition. (FDA, 21 CFR 312.32; ICH E2A and ICH E6).

**ALL SERIOUS** adverse events that meet the above criteria **MUST** be immediately reported to the sponsor within the timeframes detailed in the table below.

Hospitalization	Grade 1 and Grade 2 Timeframes	Grade 3-5 Timeframes
Resulting in Hospitalization $\geq$ 24 hrs	7 Calendar Days	24-Hour; 3 Calendar Days
Not resulting in Hospitalization $\geq$ 24 hrs	Not required	

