**Expedited AE reporting timelines are defined as:**

- “24-Hour; 3 Calendar Days” - The AE must initially be reported within 24 hours of learning of the AE, followed by a complete expedited report within 3 calendar days of the initial 24-hour report.
- “7 Calendar Days” - A complete expedited report on the AE must be submitted within 7 calendar days of learning of the AE.

Serious adverse events that occur more than 30 days after the last administration of investigational agent/intervention and have an attribution of possible, probable, or definite require reporting as follows:

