**Expedited 7 calendar day reports for:**

- Grade 2 AEs resulting in hospitalization or prolongation of hospitalization

 For studies using PET or SPECT IND agents, the AE reporting period is limited to 10 radioactive half-lives, rounded UP to the nearest whole day, after the agent/intervention was last administered. Footnote “1” above applies after this reporting period.

Effective Date: May 5, 2011

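### The expedited-reporting table in Section 8.4.1 exempts some grade 1-2 serious adverse events that the protocol's own rule says must be reported

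*Combined protocol and SAP*

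**What the plan says.** Section 8.0 makes the site principal investigator responsible for "reporting any/all serious adverse events to the sponsor as described within the protocol, regardless of attribution". The FDA reporting requirements under Section 8.4.1 list six criteria, any one of which makes an event serious; none carries a grade limit. Criterion 3 is "An adverse event that results in inpatient hospitalization or prolongation of existing hospitalization" for at least 24 hours. Criterion 4 is incapacity and criterion 5 a congenital anomaly. Criterion 6 explicitly does not depend on a hospital stay: "Important Medical Events (IME) that may not result in death, be life threatening, or require hospitalization may be considered serious". Every event that meets a criterion must "be immediately reported to the sponsor within the timeframes detailed in the table below".

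That table has two rows. One is for events resulting in hospitalization of at least 24 hours; the other is labelled "Not resulting in Hospitalization", with the same threshold. Grade 1-2 events in the first row have 7 calendar days. For grade 1-2 events in the second row, the table says that no report is needed. Neither label mentions prolongation. The footnote on related SAEs arising more than 30 days after the last dose does mention it, asking for a 7-day report of "Grade 2 AEs resulting in hospitalization or prolongation of hospitalization".

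Outside expedited reporting, Section 8.5.2.1 sends grade 1-2 events to case report forms only when they are judged at least possibly related.

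Two sets of deadlines appear. The Definitions in Section 8.0 describe expedited reports as "Events reported to sponsor within 24 hours, 5 days or 10 days of study team becoming aware of the event". Section 8.4 uses a 24-hour notice with a complete report 3 calendar days after it or, on its slower track, "A complete expedited report on the AE must be submitted within 7 calendar days of learning of the AE".

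**The concern.** The table is what site staff will consult when deciding whether to file. If it exempts events that the sentence above it makes mandatory, sites will resolve the conflict differently, and those that follow the table will leave out part of the SAEs. The population sharpens this: patients enter as inpatients (3.1.2), and the form of criterion 3 that applies to an inpatient is the one missing from the row label. SAE rates are compared between arms (13.5 item 9) and the DSMB reviews the safety data (13.7), so both depend on the capture rule being complete.

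**Working it through.** No figure in the plan needs to be reproduced. The check sets the rule beside the table and then follows an exempted event through the other reporting route.

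1. Grade 1-2 SAEs within 30 days of the last dose, by the reason they are serious:

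| Reason serious | Text of 8.0 and 8.4.1 | Table in 8.4.1 |
|---|---|---|
| Criterion 3, new hospitalization | Report | 7 calendar days |
| Criterion 3, prolonged existing stay | Report | 7 calendar days if the first label is shorthand for all of criterion 3; no report if read literally |
| Criteria 4 to 6 only | Report | No report, on either reading |

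The third line is a contradiction however the labels are read. The second depends on the reading.

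2. Who is affected. All patients are admitted at entry (3.1.2). Until discharge an event cannot cause a new admission, so criterion 3 can be met only by prolongation. After discharge a new admission is possible, and the table handles it. For a patient who completes the 14-day course, the 30-day window closes on Day 14 + 30 = Day 44, so it can include time at home.

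3. The other route. Section 8.1(g) sends expedited events to routine reporting as well, so an event exempted from the first loses that path to the second. Section 8.5.2.1 then decides. If the event is judged at least possibly related, it goes on a case report form as a grade 1-2 event. If it is judged unlikely related or unrelated, neither route asks for it.

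4. Where the data are used. Section 13.5 item 9 compares SAE rates by chi-square or Fisher's exact test, and 13.7 gives safety data to the DSMB.

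5. What is not touched. The primary endpoint rests on Day 28 status (12.0, 13.3.1), the sample size on 80% versus 92% (13.6), and the accrual suspension rule on related events of grade 3 or higher (13.7). None uses grade 1-2 SAEs.

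6. Deadlines. The Definitions give 24 hours, 5 days and 10 days; Section 8.4 gives 24 hours plus 3 days, and 7 days. Only the 24 hours is common to both. The Definitions count from awareness, whereas the 3 days in 8.4 count from the initial notice. With the notice filed at its limit, the complete report is due 1 + 3 = 4 days after awareness. Pairing the figures in order, which is an assumption because the Definitions tie 5 and 10 days to no event type, the gaps are 5 − 4 = 1 day and 10 − 7 = 3 days.

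**The case against.** The strongest reply is that the first row label is shorthand for criterion 3. It sits beneath that criterion, repeats its 24-hour threshold, and the table is introduced as the timetable for all events meeting the criteria. On that reading a grade 1-2 event that prolongs the stay has 7 days. This is plausible and reduces the prolongation part to an ambiguity. It does not settle it, because the footnote on late events spells prolongation out, and it does nothing for criteria 4 to 6.

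Several stronger readings are tempting, and the documents do not support them.

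- A reader might infer that reporting as such is waived. The exemption covers expedited reports only; related grade 1-2 events still reach case report forms, as do all events of grade 3 and above (8.5.2.2, 8.5.2.3).
- A reader might infer that every patient is an inpatient throughout. That holds at entry; footnotes l and o to the test schedule (4.0) provide for discharge.
- A reader might infer that late events are better covered than events during dosing. The late rule is more explicit about prolongation but narrower otherwise: related events only, and grade 2 only for the 7-day report.
- A reader might subtract 3 from 5 and report a 2-day gap in deadlines. The two clocks start at different points, and with the notice filed at its limit the gap is about 1 day.
- A reader might infer that sites are left with two competing deadlines. Section 8.1(e) already directs them to Section 8.4 for the timeframe, so the definition is mostly a stale entry.
- A reader might infer a bias towards one arm. The same rule applies to both arms of a double-blind trial, and the documents give no basis for a direction.

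The heading of 13.5 item 9 also refers to events related to treatment. If the comparison were confined to those, unrelated events would not enter it. The text of the item sets no such limit on the SAE rates compared.

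**Conclusion.** The table contradicts the rule it implements. For grade 1-2 events serious only under criteria 4 to 6, the conflict is certain. For grade 1-2 events that prolong the index stay, it depends on a literal reading of the label. The events at risk of being lost altogether are those among them judged unlikely related or unrelated. Their number cannot be estimated from the documents and may be small. The consequence is possible under-counting in the between-arm SAE comparison and in DSMB review. The conclusion assumes that sites follow the table and 8.5.2.1 as written. It does not rely on the grade 3-5 cell of the second row, which appears blank and may have been merged with the one above. The deadline mismatch is real but near-clerical.

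**What to change.** Reconcile the table with the seriousness criteria. In the first row, name prolongation of an existing stay alongside hospitalization, with the same 24-hour threshold. Make the second row cover events that are serious for any other reason, and replace the grade 1-2 exemption there with a reporting timeframe of the sponsor's choosing. With those two changes every grade 1-2 SAE in the window has a deadline and, through 8.1(g), also reaches routine data.

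As a minor tidy-up, rewrite the definition of expedited reporting in Section 8.0 to cite the Section 8.4 timelines, so that one set of deadlines stands.

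The cost is protocol wording and a few more expedited reports.
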